Title	Assessment of Myocardial Ischemic-Reperfusion Injury During Off- and On- Pump CABG (AMIRI-CABG) ClinicalTrials.gov Identifier: NCT03050489	
Authors *	[name]	
Trial design	Prospective non-randomized single center	
Methods		
Participants	Eligibility criteria: multivessel coronary artery disease with indications for elective coronary artery bypass grafting	
Interventions	Group 1: off-pump CABG Group 2: on-pump CABG Group 3: pump-assisted CABG (on-pump CABG without aortic cross-clamping)	
Objective	To compare level of MPO between three groups of intervention	
Primary objective	To compare ischemic-reperfusion injury between three groups of intervention	

Assessment of Myocardial Ischemic-Reperfusion Injury During Off- and On- Pump CABG  
 (ClinicalTrials.gov Identifier: NCT03050489). Corresponding author: [name]  
[[contact]](mailto:[contact]) [contact]

Date of the document 06 December 2016

Secondary objective	To assess ability of MPO to predict worse outcome (death) To assess relation between MPO and TnI	
Outcome	MPO level after CABG, death after CABG	
Randomization	Non-randomized allocation. Heart Team decision.	
Blinding (masking)	None	
Results		
Numbers randomized	Number of participants screened n=500  Allocated (non-randomized): off-pump CABG (n=181), on-pump CABG (n=128), pump-assisted CABG (n=27)	
Recruitment	Complete	
Numbers analyzed	Off-pump CABG: 181 On-pump CABG: 128 Pump-assisted CABG: 27	
Outcome	Could MPO predict death during 30 days after CABG	
Harms	Important adverse events or side effects	
Conclusions	CPB activates leucocytes that cause myocardial damage  Preoperative MPO level could evaluated as a predictor of myocardial damage and worse outcome after CABG	
Trial registration	ClinicalTrials.gov Identifier: NCT03050489	
Funding	Assessment of regenerative ability after cardiac surgery	

*Table 2 Statistical analysis synopsis*

Assessment of Myocardial Ischemic-Reperfusion Injury During Off- and On- Pump CABG ClinicalTrials.gov Identifier: NCT03050489	
Hypothesis	Ischemic – reperfusion injury are comparable between groups
Primary objective	To compare ischemic-reperfusion injury during off-pump, on-pump and pump – assisted CABG
Secondary objective	To assess ability of myeloperoxidase to predict worse outcome after CABG

Assessment of Myocardial Ischemic-Reperfusion Injury During Off- and On- Pump CABG  
 (ClinicalTrials.gov Identifier: NCT03050489). Corresponding author: [name]  
[[contact]](mailto:[contact]) [contact]

Date of the document 06 December 2016

Type of trial	Prospective non-randomised single-centre
Type of research	Exploratory
Timeline	2015-2019
Groups	Off-pump  On – pump  Pump-assisted (on-pump without aortic cross-clamping)
Sample size estimation	> 300 patients
Planned sample size	Average: 300  Off-pump: 100  On-pump: 100  Pump-assisted: 100
Actual sample size	Average: 336  Off-pump: 181 (conversion 6)  On-pump: 128  Pump-assisted: 27
Baseline characteristics comparing	Testing for type of distribution of baseline characteristics:  ANOVA for normal distribution  Kruskal-Wallis test with multiple groups comparison adjustment for non-normal distribution  Chi-squared test or exact Fisher's test for nominal data
Statistics hypothesis testing	ANOVA/ANCOVA for MPO level, troponin I level
Missing Data Handling	Drop observations with missing data
Evaluating of reason of missingness	Hypothesis: Missing data depend on severity of complications  Hypothesis testing with logistic regression model: Missingness = complications

Assessment of Myocardial Ischemic-Reperfusion Injury During Off- and On- Pump CABG  
(ClinicalTrials.gov Identifier: NCT03050489). Corresponding author: [name]  
[[contact]](mailto:[contact]) [contact]

Date of the document 06 December 2016

#### Abbreviations

AEs – Adverse events

CABG – coronary artery bypass grafting

CPB – cardiopulmonary bypass grafting

ECG – elecrocardiogram

IL-8 - interleukin 8

IQR – interquartile range

LCx – left circumflex artery

LDL - low-density lipoprotein

MPO – myeloperoxidase

Nmiss – number of missing values

RCA – right coronary artery

Rpm – rate per minute

SAE - Serious Adverse Event

URL – upper reference limit

#### Introduction

Coronary artery bypass grafting (CABG) is worldwide performed procedure. This procedure could be performed with cardiopulmonary bypass with aortic cross-clamping, without aortic cross-clamping (pump-assisted on beating heart with mechanical support of circulation) and off-pump. Some authors reported better outcomes for off-pump CABG, but others preferred on-pump CABG due to comfortable circumstances for coronary artery suture and pointed out on the risk of incomplete revascularization for off-pump CABG. Pump-assisted CABG could be favorable for myocardial tissue due to maintaining coronary flow as well as stable hemodynamics. There were a lot of clinical trials comparing short- and long-term outcomes of on-pump and off-pump CABG. But there is little evidence about comparison of myocardial damage during on-pump CABG, off-pump CABG and pump-assisted CABG. Most common timepoints for cardiac troponin level were within 2 days postoperatively. A few clinical trials monitored cardiac troponin level after second day postoperatively and lack thereof, of precise data about cardiac troponin dynamic after different types of CABG. Another important issue is inflammation response during CABG, which is lower in off-pump CABG. But latest trials reported that CPB-mediated inflammation response play a less important role than surgical wound-mediated inflammation response. It has been reported that myeloperoxidase (MPO) involved in ischemic-reperfusion myocardial damage [1]. Some clinical trials evaluated prognostic value of MPO for acute coronary syndrome [2, 9]. The goal of current clinical trial is to evaluate MPO-level during off-pump, on-pump and pump-assisted CABG as well as myocardial damage and outcomes. Serum level of MPO as it has been reported raise fast during minutes after ischemia-reperfusion and could be measured during surgical procedure and served as a predictor major adverse cardiac events [1].

# Assessment of Myocardial Ischemic-Reperfusion Injury During Off- and On- Pump CABG

(ClinicalTrials.gov Identifier: NCT03050489). Corresponding author: [name]

[[contact]](mailto:[contact]) [contact]

Date of the document 06 December 2016

Cardiac troponin is a specific and sensitive marker of myocardial necrosis and has found wide application in clinical practice. Nevertheless, the links of the pathogenesis that precede its release into the systemic circulation have not been sufficiently studied [7]. As early and specific markers of myocardial damage, MPO activated by ischemia-reperfusion of leukocytes, which are released into circulation and participate in myocardial damage, can act [7]. By measuring the concentration of inflammatory mediator MPO that degranulate the white blood cells and which can damage cardiomyocytes, it is possible to predict the extent of myocardial damage [6].

Inflammation plays a crucial role in plaque destabilization and rupture. MPO belong to the marker of plaque instability and degranulated by leukocytes and produces active forms of halogens that is an important in antibacterial protection [12]. An important advantage of MPO in comparison with other markers is the presence of intrinsic activity, which, in the presence of fluorogenic substrates, allows to shorten the time of performance of enzyme-linked immunosorbent assays to two stages - sorption of the enzyme from the sample and detection of its activity, which is especially important for emergency diagnosis . Mediators of inflammation, secreted by the activation of leukocytes after ischemia-reperfusion, contribute to myocardial damage, accelerate the development of atherosclerosis and destabilize atherosclerotic plaques[12].

At present, a large number of works are devoted to the problem of ischemic-reperfusion injury, however, the molecular-biological aspects have not been fully elucidated. A number of clinical studies of the diagnostic value of myeloperoxidase in relation to acute coronary syndrome was conducted, and the prognostic value for cardiovascular complications in patients after PCI of was studied [3 , 5]. There are also studies evaluating the concentration of MPO in the coronary sinus after restoration of blood flow in aorto-coronary bypass surgery. Modern ideas about the mechanisms of MPO-dependent modification of low-density lipoprotein (LDL), their role in initiating inflammation and destabilization of atherosclerotic plaque are presented in the following reviews [8]. In brief, the meaning of the participation of modified LDL in atherogenesis is reduced to the following. Activation of monocytes and neutrophils leads to their degranulation and release of MPO into the extracellular space. Due to its polycationic properties ( $pI > 9$ ), MPO binds to the negatively charged surface of LDL, as well as the cells of the vascular wall. As a result of activation of NADPH oxidase on the surface of leukocytes and endotheliocytes, the production of superoxide anion radical is enhanced. Spontaneous or catalyzed by the enzyme superoxide dismutase dismutation of the latter leads to the formation of hydrogen peroxide. Conditions are created for MPO-dependent synthesis of HOCl, which modifies LDL, and also causes endothelial dysfunction. Modified LDLs penetrate the damaged endothelium into the subendothelial space, where they are captured by macrophages. The accumulation of modified LDL leads to the transformation of macrophages into foam cells and the accumulation of lipids in the arterial intima. In addition, native LDL can also penetrate through the endothelium, where they undergo oxidative / halogen modifications from the active forms of halogens formed with the participation of MPO. Finally, modified LDLs activate endotheliocytes and monocytes, which results in the secretion of interleukin 8 (IL-8) and tumor necrosis factor (TNF $\alpha$ ), respectively. In turn, IL-8 and TNF $\alpha$  activate monocytes and endothelial cells, closing the vicious circle of LDL modification. Also, modified LDL, interacting with the endothelium, inhibit the fibrinolysis process, contributing to the formation and subsequent destabilization of atherosclerotic plaque. Recently, we have shown that MPO are secreted by

Assessment of Myocardial Ischemic-Reperfusion Injury During Off- and On- Pump CABG

[figure not shown]
(ClinicalTrials.gov Identifier: NCT03050489). Corresponding author: [name]

[[contact]](mailto:[contact]) [contact]

Date of the document 06 December 2016

neutrophils in response to LDL-modified oxidants . Thus, there is reason to assume the diagnostic significance of identifying active leukocyte enzymes in cardiovascular diseases [10].

## Study Design

Prospective single center non-randomized clinical trial.

**Study Centers:** First Saint Petersburg State Medical University.

**Number of groups:** 3

Intervention:

Group 1: off-pump CABG

Group 2: on-pump CABG

Group 3: pump-assisted CABG (on-pump CABG without aortic cross-clamping)

**Sample size:** >300.

*Table 3 Number of patients*

Intervention	Number of patients	
	Planned	Actual
off-pump CABG	100	181 (175)
on-pump CABG	100	128 (127)
pump-assisted CABG	100	27 (33)
Total	300	336
Conversion	N/A	6

181 patient planned for elective CABG. There were 6 conversions to pump – assisted CABG (on-pump CABG without aortic cross-clamping). 175 received off-pump-CABG. 27 patient planned for elective pump – assisted CABG (on-pump CABG without aortic cross-clamping). 33 pump – assisted CABG were performed.

**Primary Endpoint:** MPO level after operation.

**Secondary Endpoints:** low output syndrome, length of stay in intensive care unit, length of stay in hospital, inotrope and vasopressor agents demand, duration of pulmonary ventilation, end systolic volume, end diastolic volume, ejection fraction, reoperation, renal dysfunction, atrial fibrillation, death during 30 days after CABG, stroke during 30-days after CABG.

Assessment of Myocardial Ischemic-Reperfusion Injury During Off- and On- Pump CABG (ClinicalTrials.gov Identifier: NCT03050489). Corresponding author: [name] [[contact]](mailto:[contact]) [contact]

Date of the document 06 December 2016

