### **Study objectives**

- To compare ischemic-reperfusion injury after off-pump, on-pump and pump-assisted - CABG

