### **Primary objective**

- To compare MPO level before and just after performing coronary anastomosis during off-pump CABG, on-pump CABG and pump-assisted CABG (with cardiopulmonary bypass without aortic cross-clamping)
- To compare TnI level between groups

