#### **Myeloperoxidase Test**

Biomaterial production protocol:

1st test before surgery. Blood is obtained from a central venous catheter in a volume of 4 ml into a violet tube. Within 7 minutes, centrifugation at 3000 rpm at 4 ° C is carried out. The plasma is then collected into an eppendorf-type tube of 1 ml and frozen at -40 or below.

The 2nd test immediately after performing coronary artery suture. Blood is obtained from a central venous catheter in a volume of 4 ml into a violet tube. Within 7 minutes, centrifugation at 3000 rpm at 4 ° C is carried out. The plasma is then collected into an eppendorf-type tube of 1 ml and frozen at -40 or below. Samples, they are delivered to the laboratory of biochemical genetics of the Institute of Experimental Medicine, where molecular and biological studies are performed. The receipt of the material was approved by the ethical committee of the First State Medical University after I.P.Pavlov, protocol 03 / 17-11.

Earlier we worked out methods for isolating homogeneous preparations of myeloperoxidase (MPO) [11]. The preparations of MPO ( $M \sim 145$  kDa,  $RZ \sim 0.85$ ) obtained with the help of original approaches do not contain impurities of leukocyte proteinases and differ in the specific activity that exceeds commercially available analogs. For the quantitative determination of MPO, previously used solid-phase enzyme-linked immunosorbent assays will be used, which are characterized by high sensitivity and specificity due to the independent production of monovalent antibodies against the proteins.

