### Primary endpoint analysis

Hypothesis: MPO levels after procedure are different between groups.

Hypothesis testing:

- Normality test (Kolmogorov-Smirnov test, Shapiro-Wilk test)

Group comparing:

Continuous variables

- Non-normal distribution: Kruskal-Wallis test with adjustment for multiple comparisons

*Table 6 Myeloperoxidase variables specifications*

Characteristic	Variable name in database	Test
MPO level before procedure	MPOPreOp	Kruskal-Wallis test
MPO level after procedure	MPOPostOp	Kruskal-Wallis test

*Table 7 Myeloperoxidase before and during coronary artery bypass grafting (CABG)*

Variables	off-pump CABG (N=181)	on-pump CABG (N=128)	pump-assisted CABG (N=27)	P Value*
MPO before CABG				0.2904
Nmiss (%)	34 (18.8)	21 (16.4)	9 (33.3)	
Mean±SD	35.8±32.1	39.9±30.6	29.2±14.8	
Min–Max	2.8–237.8	4.0–168.9	5.6–65.4	
Median (IQR)	27.7 (17.0–41.0)	31.0 (19.0–48.7)	29.0 (18.7–34.0)	
MPO after CABG				<.0001
Nmiss (%)	28 (15.5)	26 (20.3)	13 (48.1)	

Date of the document 06 December 2016

Variables	off-pump CABG (N=181)	on-pump CABG (N=128)	pump-assisted CABG (N=27)	P Value*
Mean±SD	96.2±75.3	210.9±138.7	175.0±102.6	
Min–Max	9.1–410.3	16.7–824.6	63.4–374.5	
Median (IQR)	66.5 (41.3–135.8)	184.3 (135.0–250.0)	144.7 (95.0–284.9)	

\* Kruskal-Wallis test, Nmiss – number of missing values, SD – standard deviation, IQR – interquartile range, CABG – coronary artery bypass grafting

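### The primary endpoint is labelled post-operative MPO, but the sample is intra-operative with no stated time from reperfusion, so it is not shown to represent ischemic-reperfusion injury after CABG

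*Combined protocol and SAP*

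**What the plan says.** The combined protocol and SAP gives the primary endpoint in Study Design as "MPO level after operation". Table 1 lists the outcome as "MPO level after CABG, death after CABG", and Primary endpoint analysis sets the hypothesis "MPO levels after procedure are different between groups".

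The sampling instructions place the value elsewhere. Myeloperoxidase Test describes one sample before surgery and one during it: "The 2nd test immediately after performing coronary artery suture". Both come from a central venous catheter. Primary objective agrees with that timing: "To compare MPO level before and just after performing coronary anastomosis during off-pump CABG".

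The Introduction reports that MPO is said to "raise fast during minutes after ischemia-reperfusion" and can be measured during the operation. Study objectives states the aim as "To compare ischemic-reperfusion injury after off-pump, on-pump and pump-assisted" CABG. Definitions, under Ischemic-Reperfusion Injury, defines that injury by a troponin I rise above the reference limit in patients without type 5 infarction. MPO is not part of the definition.

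**The concern.** If MPO moves within minutes of reperfusion, as the Introduction says, the position of the sample relative to reperfusion decides what it measures. The plan fixes that position only by a suture, and the same suture can mean different things in the three arms. On-pump CABG is described as using aortic cross-clamping, and pump-assisted CABG is defined as doing without it. A sample drawn after a coronary suture could therefore fall before clamp release in the on-pump arm, a possibility that does not exist where there is no clamp.

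At stake is the reading of the primary comparison. A difference in MPO between arms could partly reflect a difference in sampling time relative to reperfusion. The post-operative label hides this, and the section headed Ischemic – reperfusion injury analysis (MPO level) presents the value as a measure of the injury itself.

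**Working it through.** The plan has no sample size calculation or stated figure to reproduce here. The check sets the sections side by side.

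1. **Places that put the value after surgery:** Study Design (primary endpoint), Table 1 (outcome), the hypothesis under Primary endpoint analysis, Table 6, the second block of rows in Table 7, Table 22 and Table 26.

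2. **Places that put it during surgery:** Primary objective, Myeloperoxidase Test, the title of Table 7, and the description of LGMPOPostOp in Table 8 (repeated in Tables 11, 14, 17 and 20). Table 7 thus disagrees with itself: its title says during, its row says after.

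3. **Which is right.** Myeloperoxidase Test describes two samples and no later one. The value analysed as post-operative can only be the second, intra-operative sample.

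4. **Which suture.** The instruction does not identify it. Patients have multivessel disease, so several anastomoses are to be expected.

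5. **Time from reperfusion.** The surgical-time variables are AoClamp, CPBTime and OpTime. All three are durations. None records when the blood was drawn or when the clamp came off, so none can place the sample before or after release.

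6. **Common landmark.** Clamp release exists only in the on-pump arm. It cannot serve all three groups, and no other reperfusion landmark is given.

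7. **Link to the injury.** The MPO model carries the injury heading, while Definitions rests the injury on troponin I. The plan does not reconcile the two.

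8. **Patients concerned.** Table 25 gives those with a second sample as 153 + 102 + 14 = 269. The on-pump share is 102/269 = 37.9%. The number of these drawn before clamp release could be anything from 0 to 102 under the rule as written.

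**The case against.** The strongest reply is that the true timing is not concealed. Primary objective, the Table 7 title and the variable descriptions all reveal it, and the Introduction gives a reason for sampling during surgery. That is fair, and a careful reader can recover the time. But the reason given supports an intra-operative name, and it makes the missing reperfusion landmark matter more.

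A second reply is that the injury objective does not depend on MPO alone. Primary objective also lists a troponin I comparison, four sections model day-1 troponin I, and Table 30 compares troponin I by group. This stands, and it is why the point can be repaired. It does not cure the MPO section's heading.

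A third reply is that a retrospective classification may be impossible, because nothing shows that draw times or clamp-release times were kept. This also stands and limits the fix.

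The Introduction's mention of the "concentration of MPO in the coronary sinus after restoration of blood flow" concerns other studies. It is no evidence of an error in this plan.

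**Conclusion.** The point holds, as a matter of labelling and of how far the primary comparison can be taken. The endpoint's name conflicts with its sampling time, the anastomosis and the interval from reperfusion are unspecified, and the value is therefore not shown to represent the injury that the plan defines by troponin I. The clamp-release question concerns up to 102 of 269 measured patients, with the affected share unknown. This rests on reading the on-pump arm as cross-clamped, as the Introduction describes it, and on there being no sampling instruction beyond the one printed.

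A reader might infer more, and the documents do not support it:

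- **That the blood was drawn at the last suture.** No section says so; which suture is part of the ambiguity.
- **That the value cannot reflect reperfusion injury.** All on-pump samples may have followed clamp release. The text leaves this open in both directions.
- **That off-pump hearts stayed perfused throughout.** The Introduction mentions maintained coronary flow only for pump-assisted CABG.
- **That the results show an effect of bypass rather than ischemia.** Median MPO is 144.7/66.5 = 2.18 times off-pump in the pump-assisted arm and 184.3/66.5 = 2.77 times in the on-pump arm. The pump-assisted figure rests on 14 of 27 patients. Missingness is 48.1% there against 20.3% on-pump, and the plan attributes missing values to readings above the assay limit. In Table 10 clamp time explains almost nothing (partial eta squared 0.0002), but neither does bypass time (0.0004). The model also includes group, which absorbs the clamped-versus-unclamped contrast. Table 10 is itself unreliable: it prints F 0.05 with p 0.3, where about 0.8 would be expected, and F 0.2 with p 0.0001.

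Second-sample MPO shows no clear association with day-1 troponin I (p 0.3, 0.2 and 0.8 in Tables 13, 16 and 19). That gives no support for treating it as the defined injury, but it does not prove a timing fault.

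**What to change.** 1. **Rename the endpoint** as intra-operative central venous MPO after coronary anastomosis in Table 1, Study Design, Primary endpoint analysis (Tables 6 and 7), Table 22 and wherever the label recurs. The site should confirm which anastomosis was used. The tables for patients without and with low cardiac output syndrome need correcting at the same time, because their post-operative MPO rows repeat the pre-operative values exactly.

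2. **Reconcile the claim with the definition.** Bring the heading of the MPO model and the wording of Study objectives into line with the troponin-based definition. Report MPO as a systemic marker during surgery, and rest the injury comparison on the troponin I analyses.

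3. **Classify the on-pump samples where records allow.** If draw and clamp-release times exist, divide up to 102 samples into before and after release, and report both classes as a sensitivity analysis. If they do not exist, state that as a limitation.

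Recruitment is complete, so no new sample can be drawn. The cost is rewording plus a record search for at most 102 patients. The price is a narrower claim for MPO, and some or all samples may prove unclassifiable.
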